## NOTICE REGARDING IMMUNOPROGRESSION

**DUE TO KNOWN PVSRIPO-MEDIATED TREATMENT EFFECTS, INCREASED TUMOR SIZE ON RADIOGRAPHIC IMAGING FOLLOWING PVSRIPO ADMINISTRATION MAY OCCUR. EXCEPT IN CASES OF IMMINENT LIFE-THREATENING EMERGENCY, CONSULT WITH SPONSOR OR THEIR DESIGNEE PRIOR TO INITIATING NON-PROTOCOL-SPECIFIED TUMOR TREATMENTS OR PERFORMING SURGICAL RESECTION.**

- PVSRIPO's immune-mediated mechanism of action (MOA) is known to result in atypical tumor imaging responses that can manifest as polycystic or pseudopressive appearance, including areas of new enhancement and tumor enlargement (termed immunoprogession) that can persist for up to 6 or more months after infusion. Thus, reliance on radiographic imaging standard criteria (eg, Immunotherapy Response Assessment for Neuro-oncology (iRANO)[1]) for determining disease progression is not optimal for PVSRIPO-based therapy; see **Table 3** for modified response criteria.
- The time to objective radiographic anti-tumor response ranged from approximately 5 to 29 months post-infusion in the Recurrent Glioblastoma (rGBM) PVSRIPO Phase 1 study (Pro00031169; median time to response 15 months).
- For patients to have the best opportunity for an immune-mediated anti-tumor response, experience suggests that patients should be managed as noted below and as outlined in the protocol.

**Treatment emergent adverse events should be managed at the discretion of the principal investigator, with patient safety being the primary consideration. Based on prior experience, the best recommended management of treatment-induced peritumoral edema or of a pseudopressive, polycystic, expansive-type of tumor appearance (ie, immunoprogession) within 6 months of any PVSRIPO infusion is as follows:**

- **Radiographic findings but patient asymptomatic/stable:**
  - Observe and continue to follow per protocol
- **Radiographic findings with new onset/worsening clinical symptoms:**
  - Preferred: Low dose bevacizumab (7.5mg/kg every (q) 3 weeks; few cycles as possible to achieve symptom control)
  - Initiation of low dose steroids (dexamethasone  $\leq$  4mg/day) if rapid response is clinically indicated
  - Other supportive care treatments, as required (eg, antiepileptics)

### Summary of Major Protocol Amendment Changes

Protocol Version and Date (from, to)	Summary of Major Changes by Section
Version 3 (23April2021) to Version 4 (21May2021)	

• Updated Table 1 to clarify timing of certain laboratory schedule of assessments and their description throughout the text.

• Updated Sections 5.2.1 and 5.2.2 to include guidance regarding platelet support both pre-infusion and prior to catheter removal.

## Protocol Synopsis

Protocol Title	A Phase 2, Open-Label, Single-Arm Study Evaluating the Efficacy, Safety and Tolerability of Oncolytic Polio/Rhinovirus Recombinant (PVSRIPO) and the Immune Checkpoint Inhibitor Pembrolizumab for the Treatment of Patients with Recurrent Glioblastoma						
Protocol Number	PVSRIPO ICI rGBM 201						
Rationale and Background	We hypothesize that PVSRIPO, a novel recombinant poliovirus (PV)/rhinovirus, oncolytic viral immunotherapeutic, when infused directly into non-immunogenic rGBM tumors, coupled with immune checkpoint inhibitors (ICI), may serve to generate a potent and specific anti-tumor response given their respective mechanisms of action. The ICI pembrolizumab is a programmed cell death receptor-1 (PD-1)-blocking antibody indicated in a number of malignancies and tumor types that has been reasonably well tolerated, with or without surgical resection, in patients with rGBM. In addition, pre-clinical data and limited clinical use outside of structured trials suggest that PVSRIPO followed by pembrolizumab may be associated with additive to synergistic anti-tumor responses [2-7].						
Objectives	
To evaluate the following after intratumoral infusion of PVSRIPO and treatment with at least one dose of pembrolizumab in rGBM patients:
 
  
 Objectives	Endpoints/Evaluation Criteria	
   
 Primary (efficacy)		
 
 Anti-tumor activity:	 
 
Objective response rate (ORR): Proportion of patients with confirmed CR or PR.
 
Duration of response (DOR): KM curves showing median DOR for all patients that have confirmed CR or PR.
 
Durable radiographic response (DRR): Proportion of patients with confirmed response (CR or PR) that lasts for <math>\geq 6</math> months. Radiographic outcomes will be assessed via iRANO criteria [1] in this protocol.
 
 	
  
	Objectives	Endpoints/Evaluation Criteria	Primary (efficacy)		Anti-tumor activity:	
 
Objective response rate (ORR): Proportion of patients with confirmed CR or PR.
 
Duration of response (DOR): KM curves showing median DOR for all patients that have confirmed CR or PR.
 
Durable radiographic response (DRR): Proportion of patients with confirmed response (CR or PR) that lasts for <math>\geq 6</math> months. Radiographic outcomes will be assessed via iRANO criteria [1] in this protocol.
 

Objectives	Endpoints/Evaluation Criteria						
Primary (efficacy)							
Anti-tumor activity:	
 
Objective response rate (ORR): Proportion of patients with confirmed CR or PR.
 
Duration of response (DOR): KM curves showing median DOR for all patients that have confirmed CR or PR.
 
Durable radiographic response (DRR): Proportion of patients with confirmed response (CR or PR) that lasts for <math>\geq 6</math> months. Radiographic outcomes will be assessed via iRANO criteria [1] in this protocol.
 
						

Primary (safety)	
Safety/tolerability:	
 
Frequency and severity of treatment-emergent adverse events (TEAE) via Common Terminology Criteria for Adverse Events (CTCAE, v5.0) for patients receiving PVSRIPO and at least one dose of pembrolizumab.
 

Secondary (efficacy)	
Anti-tumor activity:	
 
Disease Control Rate (DCR): Comprised of patients achieving CR, PR or SD for <math>\geq 6</math> months.
 
Duration of disease control (DDC): KM curves showing median DDC for patients with confirmed CR, confirmed PR or SD for <math>\geq 6</math> months.
 

Survival	
 
Overall and landmark survival: Proportion of patients alive at <math>\geq 6</math>, <math>\geq 12</math> and at 24 months post-PVSRIPO infusion as calculated by Kaplan-Meier methods.
 

Progression free survival	
 
If calculable, progression free survival (PFS) will be estimated based on the time from PVSRIPO infusion to death or confirmed progression, based on the definition of progression noted in Table 3.
 

Secondary (safety)	
	
 
Frequency and severity TEAE via CTCAE for patients receiving PVSRIPO alone without pembrolizumab (any reason).
 

Exploratory	
Identification of biomarkers of anti-tumor response to PVSRIPO followed by pembrolizumab	Assessment of tumor tissue and blood samples for identification of genetic, cytologic, histologic and/or other markers that demonstrate pharmacodynamic activity of PVSRIPO or correlate with anti-tumor response.
Alternative assessment of radiographic response/progression/PFS	Radiographic outcomes will also be analyzed as described in Table 3 for endpoint determination. All responses must be confirmed via two consecutive MRI assessments at least 4 weeks apart. If on bevacizumab therapy when response first noted, response will be confirmed $\geq 8$ weeks.
Patient-reported outcomes	Assessment of patient-reported quality of life and activities of daily living capabilities.
Study Design	This Phase 2 single-arm trial in patients with rGBM will characterize the efficacy, safety and tolerability of PVSRIPO intratumoral infusion followed by intravenous (IV) pembrolizumab 2 to 4 weeks later, and every 3 weeks, thereafter.

	
The study will begin with a safety lead-in for evaluation of dose-limiting toxicity (DLT) of the combination prior to full open enrollment. As such, the first 3 patients will be sequentially enrolled with a mandatory waiting period of 21 to 28 days after the immediate prior patient's PVSRIPO infusion to allow for DLT assessment. The DLT evaluation period will begin once a patient receives PVSRIPO followed by the first dose of pembrolizumab and continue for 21 days after the first dose of pembrolizumab (<math>\pm</math> 3 days to account for weekends, patient visit scheduling issues, etc.). The initial DLT assessment will be based on the first 3 patients, which may be expanded up to 6 patients if any DLT are noted in the first 3 (see Sections 3 and 7.4 for additional detail regarding DLT assessment).
 
The first planned dose of pembrolizumab at Week 2 will be delayed by up to 2 additional weeks in patients with any ongoing <math>\geq</math> Grade 3 peritumoral edema (PTE) or cerebral edema (CE) or <math>\geq</math> Grade 2 AEs related to PTE or CE following PVSRIPO infusion or signs or symptoms related to these events that require active treatment (eg, treatment-emergent or worsening events such as hemiparesis requiring <math>\leq</math> 4 mg/day dexamethasone or seizure requiring anti-epileptics; see Section 5.7.2), until such events resolve to <math>\leq</math> Grade 1. If such events have not resolved to <math>\leq</math> Grade 1 by Week 4 post-PVSRIPO infusion, the patient will not receive pembrolizumab under this trial and will be replaced. Pembrolizumab may be administered any time between Weeks 2 and 4 once events resolve as outlined above, as applicable. The first planned pembrolizumab treatment may also be delayed for administrative or other reasons, including other TEAE that in the Investigator's opinion warrants delayed pembrolizumab treatment, but the first pembrolizumab treatment must occur by Week 4 post-PVSRIPO infusion, as noted above.
 
In addition, if a patient requires <math>></math> 4 mg/day of dexamethasone or equivalent prior to the first dose of pembrolizumab, the patient will not receive pembrolizumab under this trial and will be replaced. These replaced patients will not be considered in the initial DLT assessment of the combination but will be eligible for additional follow-up in this study and will be summarized separately from those receiving the combination. Their information may be utilized in exploratory comparative summaries relative to patients treated with PVSRIPO and <math>\geq</math> 1 dose of pembrolizumab in this study.
 
If <math>\leq</math> 33% of the initial participants in the safety lead in (<math>\leq</math> 1 of 3 or if <math>></math> 1 patient of the first 3 experiences a DLT and 3 additional patients are included for DLT assessment, <math>\leq</math> 2 of 6 patients) experience a DLT, the twenty-four remaining participants will be enrolled. If <math>></math> 33% of participants (ie, <math>\geq</math> 3 of 6) experience a DLT, the study will be halted, and the treatment plan modified, or the study may be closed. After the DLT evaluation period and the study is open to full enrollment, ongoing monitoring of TEAEs will occur on at least a monthly basis.

Planned Number of Participants	Approximately 30 participants receiving PVSRIPO followed by pembrolizumab. Patients receiving PVSRIPO only for any reason will be followed according to the schedule of assessments with MRI and required visits occurring approximately every 9 weeks after Week 11; these patients will be replaced to achieve the approximate total of n=30 receiving PVSRIPO and pembrolizumab.
Study Entry Criteria	
Inclusion Criteria (IC):
 
 
1. <math>\geq</math> 18 years of age.
 

	
 
2. Actively growing recurrent supratentorial glioblastoma confirmed by biopsy by the site's neuropathologist or designate. 
 
○ Histologically confirmed recurrent glioblastoma within 6 weeks of PVSRIPO infusion will not require a biopsy to confirm active tumor prior to catheter placement. However, biopsy confirmation of glioblastoma must be provided if not completed within 6 weeks of catheter placement.
 
○ Progression of primary glioblastoma or transformation from a lower grade to a higher grade is acceptable for recurrence and as for primary glioblastoma, must be confirmed via prior histology by site pathologist.
 
 
 
3. Enhancing lesion <math>\geq 1</math> cm shortest diameter to <math>\leq 5.5</math> cm longest diameter in all planes, but occurrence within the prior resection cavity should not contribute to the longest diameter measurement.
 
4. Before catheter placement based on screening MRI and at the time of catheter placement via computed tomography (CT) prior to infusion, neurosurgical investigator must confirm both tumor location (<math>\geq 1</math> cm from eloquent brain) as well as placement of infusion catheter within or through the progressive enhancing tumor is feasible and at a safe distance relative to eloquent brain function, with the tip of the catheter being placed: 
 
a. Within the enhancing portion or in the vicinity of enhancement of target lesion (ie, infiltrative disease)
 
b. <math>\geq 0.5</math> cm from ventricles
 
c. <math>\geq 1</math> cm deep into the brain
 
d. <math>\geq 0.5</math> cm from the corpus callosum
 
 
Patients with ongoing neurologic symptoms with enhancing disease within 1cm of eloquent brain are excluded.
 
 
5. First or second relapse supported by MRI or CT scan; relapse is defined as progression following initial/prior therapy(ies).
 
6. Failed previous first line therapy: maximum surgical resection and radiotherapy (RT) (plus concomitant chemotherapy followed by maintenance chemotherapy if unknown or methylated O-methylguanine-DNA methyltransferase (MGMT) promoter). Patients who begin but do not complete chemotherapy/RT may still be considered for eligibility at the discretion of Sponsor.
 
7. Karnofsky performance status (KPS) <math>\geq 70</math> at screening and baseline.
 
8. Undergone prior vaccination against PV and received a boost immunization with trivalent IPOL® (PV Vaccine Inactivated) (Sanofi-Pasteur SA) at least 1 week, but less than 6 weeks, prior to administration of PVSRIPO (within 6 months of PVSRIPO retreatment). Note: Patients who are unsure of their prior vaccination status or have not been vaccinated must provide proof of vaccination and/or evidence of anti-PV immunity prior to enrollment, as applicable.
 
9. Ability to safely discontinue anti-coagulant therapy(ies) prior to biopsy/catheter placement, as required per site/surgical guidelines, in the opinion of the investigator.
 
10. Hemoglobin <math>\geq 9</math> g/dl prior to biopsy/catheter placement.
 
11. Platelet count <math>\geq 100,000/\mu\text{L}</math>, unsupported; <math>\geq 125,000/\mu\text{L}</math> (can be supported via platelet transfusion and/or with a Sponsor-approved bone marrow stimulant/colony stimulating factor, eg, romiplostim) at biopsy/catheter placement.
 

--	--

12. Absolute neutrophil count (ANC)  $\geq 1000/\mu\text{L}$  prior to biopsy/catheter placement.
13. Creatinine  $\leq 1.2 \times$  upper limit of normal (ULN) prior to biopsy/catheter placement.
14. Total bilirubin, alanine aminotransferase (ALT), aspartate aminotransferase (AST), alkaline phosphatase (ALP)  $\leq 2.5 \times$  ULN prior to biopsy/catheter placement.
15. PT and aPTT  $\leq 1.2 \times$  ULN prior to biopsy/catheter placement.
16. If undetectable anti-tetanus toxoid immunoglobulin G (ATT IgG) at screen, Tdap booster vaccine  $> 1$  week prior to biopsy/catheter placement.
17. Patients must be willing and able to understand and provide written informed consent.

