### **3.1 Safety Run-in and DLT Assessment**

This study will start with a safety run-in period. The first 3 participants will be sequentially enrolled, with a mandatory waiting period of 21 to 28 days after the immediate prior patient's PVSRIPO treatment before the next patient receives PVSRIPO. The 21- to 28-day waiting period also applies after the third patient receives PVSRIPO, prior to PVSRIPO treatment of the fourth patient.

The DLT evaluation period for the first 3 patients will begin once a patient who received PVSRIPO receives the first dose of pembrolizumab and continue for 21 days ( $\pm$  3 days to

account for variations in patient visit scheduling, weekends, etc.) after this first dose of pembrolizumab. This wait period allows sufficient time for safety review prior to the next patient receiving their first dose of pembrolizumab. If  $\geq 2$  of the first 3 patients treated with PVSRIPO followed by 1 dose of pembrolizumab experience a DLT, accrual will be halted, and the treatment plan may be modified, or the study may be closed.

If no DLT occurs in the first 3 participants, the dosing regimen will continue as planned and an additional 27 participants will be enrolled to further characterize safety and anti-tumor activity of treatment with PVSRIPO plus pembrolizumab.

However, if only 1 patient experiences a DLT of the first 3 participants treated, an additional 3 participants will be enrolled (without a waiting period between participants) to undergo DLT evaluation. If  $\leq 33\%$  of participants (ie,  $\leq 2$  of 6 total) experience a DLT, the 24 remaining participants will be enrolled. If  $> 33\%$  of participants (ie,  $\geq 3$  of 6) experience a DLT, the study will be halted, and the treatment plan modified, or the study may be closed. After the DLT evaluation period, ongoing monitoring of TEAEs will occur on at least a monthly basis by the Sponsor safety review team and by the DSMB, as specified in the safety plan and applicable charter, respectively.

If one of the first 3 (or 6) participants accrued withdraws from the study during the DLT evaluation period for reasons unrelated to the occurrence of a DLT, the participant will be replaced for the purpose of the initial DLT assessment. For details regarding events and criteria for meeting the definition of a DLT, see [Section 7.4](#).

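### The synopsis and Section 3.1 give different safety lead-in rules: at 2 DLTs in 3 patients one halts accrual and the other leaves expansion and full enrolment open

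*Protocol*

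**What the plan says.** **Protocol Section 3.1** covers every outcome in the first three patients.

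- No DLT: "an additional 27 participants will be enrolled to further characterize safety".
- One DLT: "However, if only 1 patient experiences a DLT of the first 3 participants treated, an additional 3 participants will be enrolled". Then, at two or fewer of six, "experience a DLT, the 24 remaining participants will be enrolled"; at three or more of six the study is halted.
- Two or three DLTs: if at least two "of the first 3 patients treated with PVSRIPO followed by 1 dose of pembrolizumab experience a DLT, accrual will be halted".

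**Protocol Synopsis, Study Design**, has three relevant statements.

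- The initial assessment uses three patients, "which may be expanded up to 6 patients if any DLT are noted in the first 3". The same sentence refers to Sections 3 and 7.4 for additional detail.
- The decision sentence sets a limit of 33% or fewer with a DLT. It spells this out as at most 1 of 3 or, if more than one "patient of the first 3 experiences a DLT and 3 additional patients are included for DLT assessment", at most 2 of 6. When the limit is met, those who "experience a DLT, the twenty-four remaining participants will be enrolled".
- If more than 33% of participants, glossed as three or more of six, "experience a DLT, the study will be halted, and the treatment plan modified, or the study may be closed".

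Protocol Section 7.4 and SAP Section 3.2.6 define a DLT but give no lead-in decision rule. Protocol Section 9.3 has the DSMB evaluate after the lead-in and lets the DSMB charter prevail over the protocol. The charter is not among the documents.

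**The concern.** A stopping rule should give one answer for each result. Here the result that matters most, two DLTs in the first three patients, has two. Section 3.1 stops accrual. A site or safety team working from the synopsis could treat three more patients and, if none of them had a DLT, open full enrolment at 2 of 6. The rule protects the first patients formally given the combination; before this trial, experience with it was four compassionate-use patients (Protocol Section 1.2.3).

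The texts also part at one DLT in three. There the synopsis decision sentence, taken literally, goes straight to full enrolment, while Section 3.1 requires three more patients to be assessed first.

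**Working it through.** **Counts.** The planned total is about 30. After three patients 30 − 3 = 27 remain; after six, 30 − 6 = 24. Both Section 3.1 figures are reproduced. The synopsis gives only 24, which fits a six-patient lead-in and not direct enrolment after three. The 33% limit is also reproduced: 1/3 and 2/6 are both 33.3%, and 3/6 is 50%.

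**Rules side by side.**

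| DLTs in first 3 | Section 3.1 | Synopsis, literal (more than 1) | Synopsis, trigger read as at least 1 | Synopsis, trigger read as exactly 1 |
|---|---|---|---|---|
| 0 | enrol 27 | enrol (24 stated) | enrol | enrol |
| 1 | add 3 | enrol (24 stated) | add 3 | add 3 |
| 2 | halt | add 3; enrol if 0 of next 3 | add 3; enrol if 0 of next 3 | no explicit halt; the any-DLT sentence still permits expansion |
| 3 | halt | enrolment limit out of reach | enrolment limit out of reach | enrolment limit out of reach |

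Reading the trigger as at least one keeps the conflict at 2 of 3. Reading it as exactly one removes the conflict from the decision sentence. What then remains is the permissive any-DLT sentence and the missing halt at two or more of three.

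**Size, with the trigger read as at least 1.** The documents give no DLT rate, so p is assumed. Let P0 = (1−p)³, P1 = 3p(1−p)² and P2 = 3p²(1−p) be the chances of 0, 1 and 2 DLTs in three patients.

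- Section 3.1 opens full enrolment with probability P0 + P1(P0 + P1).
- The synopsis, with expansion always used, adds P2 × P0.
- The gap is therefore P2 × P0 = 3p²(1−p)⁴.

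At p = 0.20: P0 = 0.512, P1 = 0.384, P2 = 0.096. Section 3.1 gives 0.512 + 0.384 × 0.896 = 0.856. The gap is 0.096 × 0.512 = 0.049, so the synopsis gives 0.905.

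| Assumed p | P2 (2 of 3) | P0 (0 of next 3) | Section 3.1 | Synopsis | Gap |
|---|---|---|---|---|---|
| 0.10 | 0.027 | 0.729 | 0.9652 | 0.9849 | 0.0197 |
| 0.20 | 0.096 | 0.512 | 0.8561 | 0.9052 | 0.0492 |
| 1/3 | 0.222 | 0.296 | 0.6255 | 0.6914 | 0.0658 |
| 0.40 | 0.288 | 0.216 | 0.4959 | 0.5581 | 0.0622 |
| 0.50 | 0.375 | 0.125 | 0.3125 | 0.3594 | 0.0469 |

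Differences in the last digit are rounding. Setting the derivative of 3p²(1−p)⁴ to zero gives 1 − p = 2p, so p = 1/3, and the maximum is 3 × (1/9) × (16/81) = 48/729 = 0.0658.

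Given 2 of 3, Section 3.1 never proceeds. The synopsis route proceeds with probability P0: 51% at p = 0.20 and 30% at p = 1/3.

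**The case against.** The best defence is that the synopsis is ambiguous rather than plainly permissive. Two of three is 67%, which fails the at-most-1-of-3 limit and exceeds the 33% named in the halt sentence. Expansion is optional, the synopsis sends the reader to Section 3, and Section 3.1 is complete and conservative. The DSMB also reviews the lead-in and can recommend stopping. If the trigger is a stray symbol before 1, the decision sentence agrees with Section 3.1 and the 24 remaining fits. Finally, SAP Section 6 records that the full planned sample was not enrolled, so the lead-in is probably over.

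Most of this stands, and it lowers the severity. It does not remove the mismatch. The halt sentence glosses its own threshold as three or more of six, so it does not clearly reach 2 of 3. The cross-reference is for detail and sets no precedence. The clause in Protocol Section 8 that lets the SAP govern does not help, because the SAP has no lead-in rule. Even the most favourable reading leaves the synopsis without a halt at two or more of three.

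A reader might go further and infer that the synopsis instructs the trial to continue after two DLTs in three. It does not; it leaves that route open.

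**Conclusion.** The inconsistency is in the current protocol text and needs no assumed DLT rate to establish. It is a should-fix wording correction to a safety rule.

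Its effect is bounded. With the trigger read as at least one, the probability of opening full enrolment differs by at most 6.6 points at any DLT rate, and by 4.9 points at 20%. These are upper figures for that reading: they assume that optional expansion is always used, that patients are independent with a common rate, and that the DSMB does not step in.

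Three stronger readings are not supported.

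- A fully literal reading widens the gap to between 3 points (p = 0.10: 0.9917 v 0.9652) and 23 points (p = 0.50: 0.5469 v 0.3125). The any-DLT sentence and the 24 remaining both point to a slip, so these figures should not be relied on.
- A reader might infer that patients were actually treated past two DLTs. The documents report no lead-in DLT count.
- A reader might infer that the 21- to 28-day wait between infusions must also change, because a late first pembrolizumab dose in one patient can let the next patient's planned dose fall inside the earlier DLT window. Protocol Section 5.3.1 already lets that next dose move to Week 4. With a prior dose on Day 28 and a 21-day wait, the next dose can move to Day 21 + 28 = 49, when the 21-day window closes (28 + 21 = 49). With a 28-day wait it can move to Day 56, past the close at Day 52 with the 3-day allowance. No change to infusion timing is proposed.

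**What to change.** Replace the synopsis decision text, including the any-DLT sentence, with the Section 3.1 rule:

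- 0 of 3: enrol 27 more.
- 1 of 3: add 3; then enrol 24 more at 2 or fewer of 6, or halt at 3 or more of 6.
- 2 or more of 3: halt.

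Check that the DSMB charter states the same rule, since it prevails. The cost is an amendment or clarification memo, with no extra patients or procedures.

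If the lead-in is already complete, state in the study report how many lead-in patients were DLT-evaluable, how many had a DLT, and which rule was applied. The planned DLT table (SAP Section 10, Table 14.3.1.8) covers the whole safety set, and no lead-in table is listed, so this would be one added statement.
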